5.9 Inclusion/Exclusion Criteria

See Table X. With the exception of criteria relevant to LO inclusion (criteria 3, 4, 10, & 11), inclusion/exclusion criteria reflect those consistent with PE delivery within VA. Participants must meet diagnostic criteria for PTSD,⁹¹ assessed using the gold-standard Clinician-Administered PTSD Scale for DSM-5 (CAPS-5; Item 2).³ Structured clinical interview for inclusion/exclusion criteria will be administered by trained and supervised assessors (Items 10, 11, 12).

Table x. Inclusion/exclusion criteria

Inclusions	Measure	Exclusions	Measure
1. Male or female Veterans at least 18 years old. Enrolled in VHA care.	CPRS	9. Recent suicidal or homicidal ideation with intent SCID-5-CT ¹² and/or plan that, in the judgment of the investigator, should be the focus of treatment	

2. Participant meets full DSM-5 diagnostic criteria for PTSD.		10. Hospitalized or meets DSM-5 criteria for a manic, hypomanic, or psychotic episode in the past 3 months	SCID-5-CT ¹²
3. Has an intimate partner with whom they've been in a committed relationship with for the last 6 months and have some form of contact with at least 5 days a week.	Self-report item	11. Meets DSM-5 diagnostic criteria for a severe substance use disorder in the past 3 months. Of note, subjects can be abusing or dependent upon nicotine or marijuana and still be included in the study	SCID-5-CT ¹²
4. Interested in participating weekly psychotherapy for PTSD with this person.	Self-report item	12. Moderate relationship violence between the identified partner and the Veteran, defined as one or more episodes of severe violence in the past year (e.g., punched, kicked, or beat up).	IPSVS Adapted ¹⁰⁸
5. Provides informed consent.	Self-report item	13. Partner screens positive for PTSD on a self-report instrument (PCL).	PCL-5
6. Speaks and reads English.	Self-report item	14. Having an ongoing medical condition that would interfere with ability to attend weekly treatment sessions.	Self-report item
7. Willing to have their therapy sessions recorded.	Self-report item	15. Having any planned upcoming major medical procedure or personal event over the next several months that would prevent them from attending weekly treatment sessions.	Self-report item
8. Willing and able to be seen via telehealth when in-person treatment options aren't available.	Self-report item	16. Severe cognitive impairment	CPRS
		17. Fails to complete baseline survey.	

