Relationship violence will be assessed by telephone from both Veteran and LO-report (Item 13). We will exclude Veteran participants if he/she has an underlying medical condition or a medical procedure (item 15 and 16) planned that would greatly impair their ability to participate in a weekly psychotherapy (i.e., a severe seizure disorder making weekly attendance difficult or a planned major surgery within a month of beginning treatment). This item will be assessed during the initial phone screening. Items 3, 4, 8, and 14 will also be assessed by phone screen. See materials document for screening items. We will administer a PTSD screen including the PCL-5, PHQ9, and questions regarding prior hospitalizations for MH concern, by telephone. If the loved one has (1) a PCL score above a 32, (2) a PHQ9 score of 9 or 10, and (3) they have ever had a hospitalization for MH or SUD concerns, a further case review will be conducted by a psychologist on the team. LOs and Veterans will be required to complete a baseline survey assessment before they can be randomized to a study arm. Failure to complete the baseline survey will result in study ineligibility (item 18).

We will exclude dyads in which either the Veteran or LO report moderate relationship violence (item 12), defined as one or more episodes of severe violence in the past year (e.g., kicked or beat up) on the IPSVS Adapted Scale¹⁰⁶. It would be counter-indicated for providers to proceed with PTSD treatment, without addressing ongoing significant relationship violence first. This is similar to the requirement that the patient must not be actively psychotic, manic, suicidal, or dependent on substances. Consequently, the reporting dyad member(s) will be provided with resources and referrals for IPV (see IPV risk algorithm). The dyad may be re-evaluated for eligibility when this exclusionary criteria has been resolved (i.e., one year has passed without an episode of severe violence). Finally, we can delay or end treatment, when clinically indicated, based on case review. For example, if the veteran is new to mental health care at the Minneapolis VA and

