8.0 Reporting

We will follow the VA Central IRB Table of Reporting Requirements for all issues that must be reported (i.e. summary of adverse events, unexpected problems and any actions or changes with respect to the protocol).

Adverse events (AE) include any untoward medical occurrence in a patient or clinical investigation subject administered an intervention and which does not necessarily have a causal relationship with this treatment. We will collect the following safety information (adverse events) that occurred within 7 days leading up to the final assessment.

1. Suicide attempts
2. Hospitalizations for mental health
3. Episodes of severe IPV

Therapists will be instructed to notify study staff immediately when such events occur during treatment delivery. Staff will report directly to the PI regarding any events. Therapists will also meet regularly for case consultation, where the occurrence of any of these events will be further discussed and tracked. Questions regarding the occurrence of each of these three events will be included in posttreatment assessments. Data obtained from participants will be reviewed for safety concerns. In the case of problems, the staff will discuss this with the PI.

Of note, survey reports of IPV on posttreatment and follow-up surveys will be reported when respondents endorse items consistent with severe violence. This includes the following: (1) hit my partner with a fist or something hard, (2) kicked my partner, (3) slammed my partner against something, (4) beat my partner, (5) burned my partner on purpose, (6) tried to hurt my partner by choking or suffocating him/her, or (7) used a knife or gun on my partner. Examples of serious adverse effects, according to the FDA, include death, life- threatening adverse events, suicide attempts, and hospitalization. Consequently, endorsement of items 6 or 7 will be considered a SAE. Given the population, some incidents of severe IPV are expected. Reports of moderate to severe IPV on baseline surveys are part of our exclusionary criteria (see inclusions/exclusions). Thus, severe IPV in reported in baseline surveys will not be reported as adverse events.

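### Section 8.0's survey list for severe IPV, and the SAE rule tied to it, cover only violence the respondent committed, not violence the respondent experienced

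*Combined protocol and SAP*

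**What the plan says.** Section 8.0 (Reporting) names three safety events to collect. The third is "Episodes of severe IPV", with no statement of who did what to whom. These events are collected for the seven days before the final assessment. Questions on all three are promised for the posttreatment assessments, and therapists are to tell study staff at once of any that occur while treatment is being delivered.

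The section then adds a rule for survey data: "survey reports of IPV on posttreatment and follow-up surveys will be reported when respondents endorse items consistent with severe violence". The list that follows begins "1) hit my partner with a fist or something hard, (2) kicked my partner, (3) slammed my partner against something, (4) beat my partner", goes on to burning as item 5, and ends, with items 6 and 7, "tried to hurt my partner by choking or suffocating him/her, or (7) used a knife or gun on my partner". On seriousness it says "endorsement of items 6 or 7 will be considered a SAE".

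At entry the protocol works differently. Section 5.9, Table x, item 12 excludes "Moderate relationship violence between the identified partner and the Veteran", and the text below the table says "We will exclude dyads in which either the Veteran or LO report moderate relationship violence". The label there is moderate, but both places define it by at least one severe episode in the past year. Section 5.6B (B.1) also defines severe violence without a direction, and one of its examples is a threat with a knife or gun.

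**The concern.** In every listed item the respondent is the one who acts. Applied as written, the survey rule registers a choking when the person who did it returns a survey and admits it. It does not register the report of the person who was choked. The entry criterion, by contrast, accepts a report from either member about violence between the two.

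This matters because severe IPV is one of only three safety events the trial collects and bears directly on a therapy that treats the couple together. Section 8.0 itself expects some incidents. A rule that relies on self-incriminating answers tends to undercount. It also leaves staff without a stated basis for classing a victim's report of choking or weapon use as serious. The resulting record goes to the IRB and would inform the planned randomised trial.

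**Working it through.** The plan gives no figure to reproduce, so the check is textual.

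**Step 1. Direction of each listed item (section 8.0).**

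| Item | Act | Committed by respondent | Experienced by respondent |
|---|---|---|---|
| 1 | hit | yes | no |
| 2 | kicked | yes | no |
| 3 | slammed | yes | no |
| 4 | beat | yes | no |
| 5 | burned | yes | no |
| 6 | choked or suffocated (SAE) | yes | no |
| 7 | knife or gun used (SAE) | yes | no |

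Committed: 7 of 7. Experienced: 0 of 7. Among the SAE triggers, committed: 2 of 2; experienced: 0 of 2.

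**Step 2. Follow one event through the section.** Suppose the loved one is choked by the Veteran and says so on a survey.

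| Route | Posttreatment | 3-month survey |
|---|---|---|
| Loved one's answers against the seven items | no listed item met; stated SAE rule not triggered | the same |
| Veteran's own answers | item 6, SAE, if returned and endorsed | the same |
| AE category 3 question | AE if within the seven-day window; no IPV-specific SAE rule | not promised |
| Therapist notification | AE if disclosed during treatment; no IPV-specific SAE rule | treatment has ended |

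The 3-month column reads the follow-up surveys named in the survey rule as including the 3-month survey. Table A in section 5.6A describes that assessment only as online measures.

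**Step 3. Width of the category 3 window.** Section 5.2A gives weekly sessions, typically 13 to 15. That is about 13 × 7 = 91 to 15 × 7 = 105 days. Seven days is 7/91 = 7.7% to 7/105 = 6.7% of that length. Section 6.1 allows the posttreatment survey up to four weeks after the last session, so the window may even fall wholly after treatment.

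**Step 4. Set the definitions side by side.**

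| Place | Direction | Whose report counts |
|---|---|---|
| 5.6B (B.1), severe violence | neutral | not restricted |
| 5.9, item 12 and text | between the partners | either member |
| 8.0, AE category 3 | neutral | not restricted |
| 8.0, survey list and SAE rule | committed only | the person who committed the act |

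The last row is the only one that runs one way.

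**Step 5. What one event is worth.** Section 5.6A gives 12 couples and section 5.3A gives ten. One event changes the couple-level rate by 1/12 = 8.3 or 1/10 = 10 percentage points.

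**The case against.** The strongest answer is that section 8.0 has other routes. Category 3 is a listed AE with no direction, it is asked about at posttreatment, and therapists must report such events during treatment. A reader might infer from the item list that a victim's report leads to no AE at all. The documents do not support that: being beaten or choked can be recorded under category 3. This part of the objection stands. It does not reach SAE classification, events outside the seven-day window that no therapist hears of, or the 3-month survey.

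Second, the list is introduced as what the rule includes, which may not be exhaustive, and the SAE sentence follows general examples that cover life-threatening events. Staff could reasonably class a victim's report as serious. That is fair, but it rests on inference, whereas the one explicit IPV rule names items 6 and 7 as worded.

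Third, the survey itself is in a Materials document that was not available for review. Section 5.6B explains why staff will not approach IPV victims uninvited about survey answers, which suggests that surveys may already ask about violence experienced. If so, only the rule needs changing.

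Fourth, disclosure is not confined to joint sessions. Section 5.6B has study providers discuss reported IPV privately with the reporter, and respondents may contact staff about their answers. Both partners are also surveyed. These routes help, but they depend on the victim making contact or on the other partner's admission.

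Finally, a reader might blame the perpetrator wording for missing a threat with a weapon. It is not the cause: item 7 concerns use, and threats are listed in neither direction.

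**Conclusion.** The point holds for the itemised survey list and its SAE rule. All seven items and both SAE triggers cover only acts the respondent committed. This does not match category 3 in the same section, or sections 5.6B and 5.9. The gap is clearest for SAE classification and at the 3-month survey.

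It would go too far to say that the trial will report a falsely clean IPV record. The documents give no rates of survey response or of reporting by either partner, so the undercount cannot be estimated. What can be said is that in a sample of 10 to 12 couples a single missed event is material.

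The conclusion assumes that section 8.0 is applied as worded and that its follow-up surveys include the 3-month survey. It does not depend on whether the survey already has items on violence experienced, since the rule as written would not use them.

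**What to change.** In section 8.0:

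- State that a severe IPV report is endorsement, by either member of the couple, of any of the seven acts in either direction (committed or experienced).
- State that either direction of item 6 or 7 meets the SAE rule.
- Apply both statements explicitly to the posttreatment and the 3-month surveys.
- Check the Materials document. Add a mirror item for each act (done to me by my partner) only where it is missing.
- When reporting events, say whether one or both members reported each.

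Separately, reconcile item 7, which covers only use of a knife or gun, with section 5.6B, which counts a threat with one as severe violence. Mirror items alone would leave that mismatch in place.

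The cost is a change of protocol wording and at most seven more survey items per respondent. The reported event count may rise.

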9.0 Privacy and Confidentiality

Protected Health Information will need accessed for the conduct of this study, but PHI will not be disclosed. Steps to ensure confidentiality and secure data are described below.

9.1 Confidentiality

For all participants, strict confidentiality procedures will be maintained to minimize the potential risk of loss of confidentiality. Participant privacy will be further assured by conducting interviews in a private office and by assigning arbitrary identifiers in place of individual names in the field notes. Data analysis, interpretation, and reporting will be based on these de-identified field notes and transcriptions. Since subject responses will not be linked to identifying information, participant confidentiality will be assured. The time commitment will be explained to all participants prior to their participation in the study. Every effort will be made to minimize the length of time and maximize the convenience of the interviews. Participants will be assured that participation is completely voluntary and that they have the right to stop participation, decline answering any questions, or change the course of the interviews for any reason, including potential feelings of discomfort.

9.2 Data Security

All data will be stored on the servers of the Center for Chronic Diseases Outcomes Research (CCDOR) at the Minneapolis VAHCS. CCDOR has well-established procedures to protect the privacy of research participants. Names, social security numbers, and contact information will not appear on any study materials. Instead, only unique study identification numbers randomly assigned to each unique record will be used. Only study team members and study programmers (when extracting data to obtain treatment adherence and compare survey responders to non-responders for the survey) will have access to an encrypted crosswalk table linking study identification numbers to identifying information. The CCDOR Statistical and Data Management (SDM) team, in partnership with IRM staff, maintain several secure servers, access to which is granted only to SDM members who have been screened and assigned appropriate security clearance to work with patient data. One common-access server contains individual project data. Access to individual project data on this server is granted only to project staff by an SDM team member, as authorized by the study investigator. Identifiers will be destroyed as quickly as possible. Audio and video recordings will be stored digitally on CCDOR servers and only accessible to the principal investigator and project coordinator. Participants will be asked not to use last names or provide identifying information during recorded interviews.

CCDOR protects data collected for the purpose of conducting research projects at a level higher than that provided for clinical encounters. We use “stand-alone,” secure data servers that are accessible only to designated, security-cleared, and trained personnel and data are de-identified as quickly as is feasible. Details about CCDOR’s specific data privacy assurance procedures to be employed for this study are provided below.

9.2A. Maintaining Secure Servers.

CCDOR maintains three secure computer servers that are protected under the Minneapolis VA Windows 2000 network. All individuals with administrative access privileges to CCDOR's servers, including IRM personnel and the CCDOR Statistical & Data Management Team, have been screened and assigned a security clearance putting them in trusted positions of the hospital with clearances to work with patient level data. These individuals and their access to the CCDOR servers is ultimately monitored and controlled by [name], Senior Program Analyst for the CCDOR Statistical & Data Management Team. IRM's access to the data is strictly limited to backing up server data, which prevents catastrophic loss of data. Backups are written to tapes that are stored in a secure location accessible only to IRM personnel. CCDOR's Statistical & Data Management Team members maintain permissions, data storage, and all server applications.

9.2A.1 Organization and Access to Research Data. With the exception of one server, named the "CCDOR Server," only the CCDOR Statistical & Data Management Team has access to remaining Center servers. Data on the "CCDOR Server" are organized by projects within folders designated by each investigator. Only members of a given project have access to a specific project folder on the "CCDOR Server." Even then, access to project data is obtained through Windows authentication (i.e., user's name and password to the network). It is virtually impossible for any person without a login name and password to the VA hospital's domain network to access data on the Center's servers. Thus, all data housed on the "CCDOR Server" are extremely secure, and access by unauthorized persons highly unlikely. Data containing patient identifying information are not stored on the CCDOR Server but are stored on the servers accessible only to CCDOR Statistical & Data Management Team members who are directly involved in the project. Thus, not even the PI can link individual names to their PHI without first obtaining permission to do so from the Statistical & Data Management Team. These protections exceed the usual protections provided PHI by the VA system.

9.2A.2 Securing Confidential Research Data. Data collected for individual Center projects are often obtained through primary (e.g., surveys) or secondary (e.g., VISTA and Austin databases) sources. All extractions of secondary data collection are stored on servers accessible to the CCDOR Statistical & Data Management Team only. Secondary data used for a study are de-identified according to HIPAA criteria and provided a random study identification number. A crosswalk table is created linking the study id with the primary key of the secondary data source. These data are only accessible to those employees of the Statistical & Data Management Team who have undergone the necessary security background checks, received appropriate security clearances, and are an integral part of an IRB-approved study. Primary data that involves surveys contain only the coded study identification number to identify study participants. The paper version of these forms/surveys is kept in locked cabinets within a locked room. Data from these surveys/forms are scanned or data entered by project staff or CCDOR Statistical & Data Management Team members to a secure folder. This secure folder is on a server accessible only to the CCDOR Statistical & Data Management Team members directly involved in the study. This protects the integrity of the data as well as its confidentiality. Primary data collection involving direct data entry is performed through a custom application written by a CCDOR Statistical & Data Management Team programmer. This ensures that data is located in

a secure environment and accessible to only those individuals with permission to access the data. Only individuals with a need to access the data, as vetted by the project's Principal Investigator are granted access. Even then, only the absolute minimum number of data elements is released.

9.2B. Data Used for Analysis.

For all projects conducted in CCDOR, the final quantitative data is constructed in Statistical Analysis Software (SAS) data sets. Qualitative data includes audio recordings of interviews that are transcribed and then stripped of all identifiers. De-identified transcripts are then uploaded into qualitative analysis software (NVIVO). Quantitative analyses are mostly conducted by statisticians assigned to the project or by other members of the project (e.g. Principal Investigator). Qualitative analyses are conducted by study investigators with qualitative expertise (e.g., [name] and study PI).

SAS data sets and qualitative transcripts will be de-identified according to HIPAA criteria, using only subjects' coded identification number as the primary key. The de-identified data set will be made accessible to those project members who are conducting analyses. Only the data elements required for the analysis under consideration are released. In summary, a separate workspace on a server accessible only to project Statistical & Data Management Team members will be created to work with administrative data. Any of the administrative data containing patient level data will be encrypted when not being used by a project programmer. All patient-identifying information will be removed from the administrative records. Upon completion of all study data, de-identified analysis data sets will be created in SAS and NVIVO that will use the subjects' coded study identification numbers as the only key.

10.0 Communication Plan

P.I. [name] will meet regularly with [name], the project manager. At these meetings, [name] will check in with [name] to ensure that the following key communications occur:

1. Ensure that required approvals are obtained
2. IRB of any Serious Adverse Events, Unanticipated Problems, or interim results that may impact conduct of the study.
3. Notify facility directors when the study reaches the point that it no longer requires engagement of the local facility

The study team will also review relevant sections of the protocol periodically, so that we can make sure that the phases of the study are conducted according to the IRB-approved protocol.

